# Benefits of Enhanced Terminal Room (BETR) Disinfection Study Study Protocol and Analysis Plan

## 1. INTRODUCTION

This document describes the main protocol components and statistical analysis plan (SAP) for the primary manuscript for the Phase 2 of "A Four-Arm Prospective, Multicenter Study to Assess the Clinical Efficacy, Effectiveness, and Feasibility of Enhanced Room Disinfection with Chlorine and UV Light Using Clinical and Microbiologic Outcomes," funded by the CDC Prevention Epicenters Program (U54CK000164).

## 2. STUDY OBJECTIVES

The primary objective of the study is to determine whether enhanced terminal room disinfection strategies will decrease the clinical risk of acquisition and infection due to multidrug-resistant organism (MDROs) in clinical practice. The specific hypotheses are:

- 1. Enhanced terminal room disinfection strategies will decrease the overall risk of acquisition and infection due to the "BIG 4": MRSA, VRE, C. difficile, and MDR-Acinetobacter (MDRAB).
- 2. Enhanced terminal room disinfection strategies will decrease the risk of acquisition and infection for each of the components of the BIG 4.

## 3. STUDY ENDPOINTS

**a. Primary endpoints:** The study includes two primary endpoints. For the purposes of power calculations and defining a primary statistical outcome, we will be analyzing the composite outcome of "first positivity" of acquisition and infection with MRSA, VRE, *C. difficile*, and MDRAB among patients considered to be "exposed" according to our inclusion criteria. This outcome will be determined by combining bed flow and microbiological data from study hospitals. In light of our a priori belief that the spore-forming organism *C. difficile* is more likely to spread through environmental means than vegetative bacteria, our second primary outcome is "first positivity" specifically of *C. difficile*.

## b. Secondary endpoints:

- 1. First positivity Exposed patients. These secondary outcomes will include the clinical incidence of individual pathogens among exposed patients as determined by data obtained from microbiological laboratories in study hospitals.
  - a. Incidence of first positivity of MRSA among exposed patients
  - b. Incidence of first positivity of VRE among exposed patients
  - c. Incidence of first positivity of MDRAB among exposed patients
- 2. First positivity Entire hospital. These secondary outcomes will include the clinical incidence of target pathogens (collectively and individually) among all patients admitted to the study hospitals as determined by data obtained from microbiological laboratories in study hospitals.
  - a. Incidence of first positivity of BIG 4 for entire hospital
  - b. Incidence of first positivity of MRSA for entire hospital
  - c. Incidence of first positivity of VRE for entire hospital
  - d. Incidence of first positivity of CDI for entire hospital

e. Incidence of first positivity of MDRAB for entire hospital

## 3. Adverse outcomes

- a. Missed opportunities rate and description. We will summarize the number of times a UV-C device failed to be used and, if available, the reason it wasn't used.
- b. Time on diversion days per 6-month study period, as determined using bed control administrative logs from study hospitals.
- c. Emergency room wait time minutes per patient, as determined using bed flow data from study hospitals.
- d. Questionnaire results HCW perception of cleaning methods
- e. Room cleaning time minutes per room, as determined using bed flow and environmental services work flow datasets from study hospitals.

The term "first positivity" is defined as the first time (either colonization or infection) a clinical culture grows MRSA, VRE, *C difficile*, or MDRAB in an exposed patient. The terms "first positivity" and "clinical incidence" are used interchangeably (Ellingson, Jernigan ICHE 2011; Cohen ICHE 2008). Clinical incidence is the most appropriate term, as our data relied on routine clinical activities. While we use the term "patient-level" analyses, all analyses are actually at the hospital level. We changed the number of patients' data included in analyses by either including only those who met our criteria as exposed (i.e., primary outcomes and secondary outcomes b.1.) or all patients in the hospital (i.e., secondary outcomes b.2.). In both instances, patients could have had multiple admissions and, potentially, multiple exposures.

## 4. STUDY METHODS

## a. Overall study design and plan

The study was designed as a pragmatic, prospective, multicenter, cluster-randomized, crossover trial with 2x2 factorial design to evaluate four different strategies for terminal room disinfection in nine study hospitals. The 28-month study period took place from April 2012 to July 2014. The 28-month period was separated into four 7-month study periods. Each study period consisted of a 1-month "wash in" period during which hospitals implemented and refined protocols followed by a 6-month period of data collection (Figure 1).

[figure not shown]

Figure 1. Schematic of crossover design. Each institution will randomly receive four interventions over the course of the 28-month study period. The first month of each intervention will be considered a "wash-out" month and surveillance data will not be counted (black boxes).

## b. Intervention

Each hospital will perform cleaning and disinfection of targeted rooms using four disinfection protocols: A) standard terminal disinfection using quaternary ammonium; B) enhanced disinfection with quaternary ammonium and UV device; C) enhanced disinfection with bleach; D) enhanced disinfection with bleach and UV device (Figure 2). The intervention is performed on the room. From a practical, implementation perspective, the cleaning strategies will be applied to contact precautions. From an analysis perspective, eligible rooms will include any room from which a) a patient with infection due to MRSA, VRE, CDI, or MDRAB has been transferred or discharged or b) a patient with known colonization with MRSA, VRE, and MDRAB has been transferred or discharged and c) the patient remained in the room for >24 hours prior to transfer or discharge.

Figure 2. 2x2 Factorial Design

		UV-C emitting device	
		No	Yes
Chemical Disinfectant	Quaternary ammonium- containing solution except hypochlorite (bleach)- containing solution for C. difficile rooms	Α	В
Chemical D	Hypochlorite (bleach)- containing solution	С	D

## d. Randomization

Randomization occurred at the level of the hospital. All hospitals used each of the four strategies an equal amount of time. The order in which the four protocols were utilized was randomly assigned to each study hospital (Figure 3). Randomization was performed by random number generators for each hospital.

Hospital Study Phase 1 Study Phase 2 Study Phase 3 Study Phase 4 1 2 3 4 5 6 7 8 8 9 10 11 12 1 2 3 4 5 6 7 8 9 10 11 12 1 2 3 4 5 6 Month Year Wash In Quaternary ammomium except bleach for *C. difficile* rooms (Reference) Quaternary ammomium + UV except bleach + UV for *C. difficile* rooms Bleach Bleach + UV

Figure 3. Randomization scheme for 9 study hospitals

## e. Blinding

Because of the nature of the strategies being evaluated in this study, blinding of the assignment of the hospital was impossible. Investigators, environmental service personnel, and infection prevention personnel were aware of the assignment in order to effectively implement and monitor the intervention.

#### 5. ANALYSIS POPULATIONS

No hospitals dropped out of the study. Data will be obtained from all patients admitted to acute care or intensive care beds in all study hospitals. Data will not be obtained from patients admitted only to emergency room or other non-acute care locations.

a. **Inclusion** - Patient stays with duration greater or equal to 24 hours will be included in the analyses.

b. **Exclusion** - Wash-in periods will be excluded from the analyses. Patient stays where a patient had prior community-acquired infection (diagnosed within 48 hours from hospitalization) or a microbiologically proven history of infection or colonization with the same target MDRO during the 12 months prior to the admission will be excluded.

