## b. Incident cases and exposure-days

- 1. A seed room was defined as a room containing a patient with microbiologically proven current or history of infection or colonization with one or more target MDROs (i.e., potentially "seeded" by the inhabitant).
- 2. Exposed patient The next patient admitted to the seed room was an "exposed patient."
- 3. Incident case Exposed patients qualified as a potential "incident case" of acquisition if they met the following criteria:
  - In seed room for ≥24 hours AND
  - A positive clinical culture with one of the target MDROs AND
  - The organism identified in the clinical culture was the same target MDRO isolated from the preceding patient in the seed room AND
  - The positive culture was obtained during the index admission either during or after exposure to the seed room *OR*
  - The positive culture was obtained during hospital readmission
    - Within 90 days of discharge for MRSA, VRE, and MDR Acinetobacter
       OR
    - Within 28 days of discharge for C. difficile
- 4. Exposure days Exposure days were calculated as the number of days the exposed patient spent in the seed room. Patients excluded from the numerator were also excluded from the denominator.

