## 13. CHANGES TO ANALYSES PLANNED IN THE PROTOCOL/GRANT

Our initial protocol and grant submission focused on outcomes that specifically met CDC criteria for a healthcare-associated infection (HAI). After discussions with the CDC at the beginning of the grant cycle (prior to study initiation), we elected to change the primary focus of the study from HAIs to "clinical incidence," as described above. This change was performed to overcome potential issues related to differences in HAI surveillance techniques across hospitals and to improve the plausibility of our outcomes.

No sensitivity analyses were originally planned. During the course of the study, however, we began to wonder about the impact of the inclusion criterion requiring 24 hours of "exposure" to the seed room—an arbitrary choice by our team at the beginning of the study to ensure the patients exposed to the seed rooms had a true exposure to the environment. As a result, we repeated our primary analyses without this requirement as a post hoc sensitivity analysis.

Finally, one of our adverse outcomes, ER wait time, was modified during the course of the study. Our initial intention was to measure and report the specific time between when the decision was made to admit the patient and when the patient left the ER to go to a hospital room. These data proved too challenging to acquire for some study hospitals. As a result, we accepted "total time in the ER," defined as the time from arrival to the ER to when the patient left the ER to go to a hospital, as a proxy measure for our initial outcome.

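### The 48-hour present-on-admission exclusion names infection only, so colonization cultured early in a patient admitted directly to a seed room counts as an acquisition and dilutes the BIG 4 composite

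*SAP*

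**What the plan says.** Section 5b has two patient-level exclusions, with different coverage. Their wording begins: "Patient stays where a patient had prior community-acquired infection (diagnosed within 48 hours from hospitalization) or a microbiologically proven history of infection or colonization". In the early arm, colonization is not named. The history arm removes stays with "a microbiologically proven history of infection or colonization with the same target MDRO during the 12 months prior to the admission will be excluded"; it names colonization but looks only at the time before admission.

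The endpoint is wider than the early arm. In Section 3b, first positivity "is defined as the first time (either colonization or infection) a clinical culture grows MRSA, VRE" or one of the other two target organisms.

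Section 6b sets the remaining conditions for an incident case:
- Exposure: "The next patient admitted to the seed room was an" exposed patient. No earlier negative culture is required.
- Time in the room: "In seed room for ≥24 hours".
- Organism: the same target organism as the preceding occupant's.
- Timing: "The positive culture was obtained during the index admission either during or after exposure to the seed room", or on readmission within 90 days (28 days for C. difficile).

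Section 6b.4 applies numerator exclusions to the denominator too. Section 6d carries the same exclusions into the hospital-wide outcomes.

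**The concern.** A present-on-admission filter should cover the same kinds of event as the endpoint. This one does not: colonization first cultured in the opening 48 hours of the index admission falls between the two arms. If the patient went directly into a seed room, that culture was taken during exposure and qualifies.

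Such a case is very likely carriage brought in from outside, which terminal disinfection of the room cannot prevent. Because the rule is the same under all four strategies, these cases form a background that no strategy can reduce. They move the composite rate ratio toward 1 and cost power.

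**Working it through.** **Step 1: trace one patient through the rules.** Take a patient admitted directly to an MRSA seed room who stays more than 24 hours, has no MRSA on record in the past 12 months, and has a clinical culture on day 1 that grows MRSA as colonization.

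| Rule | Result |
|---|---|
| 5b, 48-hour arm | Not excluded: colonization, not infection |
| 5b, 12-month arm | Not excluded: nothing proven before admission |
| 6b.2, exposed patient | Met |
| 6b.3, at least 24 hours in room | Met; a rule on length of stay, not on time to culture |
| 6b.3, same organism | Met |
| 6b.3, culture during or after exposure | Met; no minimum interval after room entry |
| 3b, colonization or infection | Met |

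The patient counts as an incident case, and no other section prevents it. A first positive culture taken before entry to the seed room is a different matter, since it was not taken during or after exposure.

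**Step 2: the planning figures.** Section 10a gives 7,000 exposed patients, so 7,000/4 = 1,750 per strategy; a baseline of 11%; a detectable absolute decrease of 3 points; two-sided 0.05; and a stated power of 80%.
- Cases: 0.11 × 1,750 = 192.5 and 0.08 × 1,750 = 140. The SAP's own count of baseline cases is 190.
- Rate ratio: 140/192.5 = 0.727.
- Poisson power = Φ(|ln RR| / √(1/m₁ + 1/m₂) − 1.96), with m₁ and m₂ the expected cases and equal exposure days assumed. Here 0.3185 / √(1/192.5 + 1/140) = 0.3185/0.1111 = 2.867, and Φ(0.907) = 81.8%.
- A pooled two-proportion test on the same figures gives 85.7%. The difference detectable with 80% power is then 2.79 points, which rounds to the stated 3.

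**Step 3: dilution.** Let q be the share of counted reference-strategy cases that enter through this gap, with the same number under the enhanced strategy. Then RR_obs = q + (1 − q) × 0.727, with m₁ = 192.5 and m₂ = 192.5 × RR_obs. The documents do not give q, so the values below are assumptions.

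| q | RR_obs | Poisson power as written | Poisson power with those cases removed (RR 0.727, m₁ = 192.5 × (1 − q)) |
|---|---|---|---|
| 0 | 0.727 | 81.8% | 81.8% |
| 1% | 0.730 | 81.0% | 81.4% |
| 2% | 0.733 | 80.1% | 81.0% |
| 5% | 0.741 | 77.5% | 79.8% |
| 10% | 0.755 | 72.7% | 77.6% |

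The two-proportion test gives the same rate ratios and the same pattern at a higher level: 81.8% as written and 83.7% after removal at q = 5%; 77.2% and 81.6% at q = 10%.

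**Step 4: what removal cannot reach.** The last column concerns only cases cultured within 48 hours. Suppose instead that 10% of counted cases are imported carriage and half of it is first cultured later (an assumption). After the fix, m₁ = 0.95 × 192.5 = 182.9, RR = (0.05 + 0.90 × 0.727)/0.95 = 0.742, and power is 75.1%.

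**The case against.** The best defence is that the gap is narrow. It needs direct admission to a seed room, an early clinical culture that is colonization and not infection, a match with the preceding occupant's organism, at least 24 hours in the room, and no proven 12-month history. Section 3b says the data came from routine clinical activities, and the SAP describes no admission screening that feeds the endpoint. At q = 1% to 2%, power drops by less than 2 points. The Poisson and two-proportion formulas differ by about 4 points, as much as the fix recovers at q = 5% to 10%. All of this stands. It limits the size of the problem, not its existence.

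One could also say that infection was meant loosely, to include colonization. The text does not support this, because the same sentence writes infection or colonization in its other arm.

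A reader might infer more than the SAP supports:
- **That the gap favours one strategy.** The rule is the same under all four, so the expected effect is dilution, unless early culturing differs by phase, and nothing in the SAP says that it does.
- **That both primary endpoints are equally affected.** Section 4b lists known colonization for MRSA, VRE and MDRAB, while C. difficile appears only as infection. The effect therefore falls mainly on the composite, although the wording in 3b covers all four organisms.
- **That the infection-only arm adds differences between hospitals.** Section 13 cites "differences in HAI surveillance techniques across hospitals" as a reason for leaving HAI outcomes, but it does not discuss this exclusion, and no section describes how infection is separated from colonization here. Every hospital also uses all four strategies and hospital is in the model, so stable differences would largely cancel.

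**Conclusion.** The point holds as a mismatch between the 48-hour exclusion and the endpoint. It follows from the wording alone. Its consequence is conservative dilution of the BIG 4 composite among exposed patients: a planned rate ratio of 0.727 would read 0.730 to 0.755, and power of 82% would fall to between 81% and 73%, if 1% to 10% of counted cases enter this way. That range is illustrative. It assumes equal exposure days per strategy, independent Poisson counts and the Section 10a planning rates, and the documents contain no figure for the share. The conditions for entry are strict, so the low end may be nearer the truth, but the documents cannot settle it. The correction is worth making because it is cheap and removes misclassified events.

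**What to change.** Reword the 48-hour arm of Section 5b to exclude, from numerator and denominator, any index-admission stay with a positive clinical test for the same target MDRO, whether infection or colonization, collected within 48 hours of the index hospitalization. State that this does not apply to readmission cultures that count under 6b.3. Without that limit, a positive found in the first two days of a readmission could be removed, although 6b.3 intends to count it.

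The cost is one line of SAP text and a query on admission and culture dates. The rule then needs no judgement between infection and colonization. A few cases and their exposure days are lost, including any genuine acquisition cultured within 48 hours. Carriage first cultured after 48 hours would remain, so the fix reduces the dilution and does not guarantee a return to 0.727.

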## 6. DERIVED AND COMPUTED VARIABLES

## a. General strategy for aggregating data at the hospital level

All variables were collected and calculated during all four study phases at each study hospital. Variables were calculated and/or summarized for each of the disinfection strategies/phases individually.

## b. Incident cases and exposure-days

- 1. A seed room was defined as a room containing a patient with microbiologically proven current or history of infection or colonization with one or more target MDROs (i.e., potentially "seeded" by the inhabitant).
- 2. Exposed patient The next patient admitted to the seed room was an "exposed patient."
- 3. Incident case Exposed patients qualified as a potential "incident case" of acquisition if they met the following criteria:
  - In seed room for ≥24 hours AND
  - A positive clinical culture with one of the target MDROs AND
  - The organism identified in the clinical culture was the same target MDRO isolated from the preceding patient in the seed room AND
  - The positive culture was obtained during the index admission either during or after exposure to the seed room *OR*
  - The positive culture was obtained during hospital readmission
    - Within 90 days of discharge for MRSA, VRE, and MDR Acinetobacter
       OR
    - Within 28 days of discharge for C. difficile
- 4. Exposure days Exposure days were calculated as the number of days the exposed patient spent in the seed room. Patients excluded from the numerator were also excluded from the denominator.

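### The 24-hour exposure rule in Section 6b.3 counts total time in the seed room, not time before the culture, so a culture taken shortly after room entry can count as an acquisition from that room

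*SAP*

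**What the plan says.** SAP Section 6b.3 joins the case criteria with AND. The patient must have been "In seed room for ≥24 hours AND" the culture must grow the preceding occupant's organism ("The organism identified in the clinical culture was the same target MDRO isolated from the preceding patient in the seed room AND"), and its timing is acceptable if "The positive culture was obtained during the index admission either during or after exposure to the seed room". A culture at readmission, within 90 or 28 days of discharge depending on the organism, is the alternative.

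Section 13 calls the 24 hours an arbitrary choice, made "to ensure the patients exposed to the seed rooms had a true exposure to the environment". The one sensitivity analysis concerning this rule is described there: "we repeated our primary analyses without this requirement as a post hoc sensitivity analysis".

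Section 5b removes two groups. The first is "Patient stays where a patient had prior community-acquired infection (diagnosed within 48 hours from hospitalization"). The second is stays with a "microbiologically proven history of infection or colonization with the same target MDRO during the 12 months prior to the admission will be excluded". Section 3 defines first positivity as colonization or infection.

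The denominator in Section 6b.4 runs from room entry: "Exposure days were calculated as the number of days the exposed patient spent in the seed room". The same item takes patients excluded from the numerator out of the denominator. The definition feeds both primary endpoints, the four-organism composite and *C. difficile* (Sections 3a and 6c).

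**The concern.** The 24 hours and the culture are not put in order. For a culture taken after the patient has left the room, or at readmission, the order follows by itself. For a culture taken while the patient is still in the room it does not, because hours spent there afterwards count toward the 24.

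A patient transferred into a seed room on hospital day 5 and cultured an hour later meets every criterion if the organism matches and the stay later reaches 24 hours. An organism detected that early is unlikely to have come from that room, so how the room was cleaned can hardly have influenced the case. If such cases form a fixed background under all four strategies, they dilute the rate ratio for both primary endpoints and cost power.

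**Working it through.** **1. Does another rule close the gap?**

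| Rule | Clock or test | What it leaves open |
|---|---|---|
| 6b.3, 24 hours | Total time in the seed room | Cultures taken early in a stay that later reaches 24 h |
| 5b, 48 hours | From hospitalization; infection only | Patients moved in later; possibly early colonization cultures |
| 5b, 12 months | Before admission | Says nothing about time from room entry |
| 6b.3, organism match | Same organism as preceding occupant | Reduces the number of such cases; does not fix timing |
| 13, sensitivity analysis | Drops the 24 hours | Loosens the definition, so cannot test this point |

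None sets a minimum interval from room entry to culture.

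**2. The plan's own power figure.** Inputs from SAP Section 10a: 190 reference cases among 1,750 patients (11%), an absolute decrease of 3% (11% to 8%), two-sided 0.05, stated power 80%.
- Ratio R = 8/11 = 0.727.
- Independent Poisson counts: SE of the log ratio = √(1/190 + 1/(190 × 0.727)) = 0.1118.
- z = 0.3185/0.1118 = 2.848, and 2.848 − 1.960 = 0.888, so power is 81.3%. This agrees with the stated 80%.
- A two-proportion calculation (1,750 per strategy, 11% vs 8%) gives 85.7%.

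Both ignore clustering by hospital.

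**3. Effect of early cases.** Let f be the share of reference cases whose culture is too early to come from the room; f is an assumption, not in the SAP. If these cases are equally frequent under all strategies and do not respond to them:

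observed ratio = f × 1 + (1 − f) × 0.727

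| f | Observed ratio | Poisson power, kept | Poisson power, removed | Two-proportion, kept | Two-proportion, removed |
|---|---|---|---|---|---|
| 0 | 0.727 | 81.3% | – | 85.7% | – |
| 5% | 0.05 + 0.95 × 0.727 = 0.741 | 76.9% | 79.3% | 81.8% | 83.7% |
| 10% | 0.10 + 0.90 × 0.727 = 0.755 | 72.1% | 77.1% | 77.2% | 81.5% |

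Removal restores 0.727 with (1 − f) × 190 reference cases.

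**4. Why 5% and 10% serve as illustrations.** Assume a constant culture rate, mean room stays of 4 to 7 days and half of all cases found in the room (none of this is in the SAP). The share of all cases cultured in the first 24 hours is then ½ × (1 − e^(−1/7)) = 7% to ½ × (1 − e^(−1/4)) = 11%. That makes no allowance for Section 5b. If only the 30–50% of exposed patients moved in later remained open to it (again an assumption), the range is about 0.3 × 7% = 2% to 0.5 × 11% = 6%. Early colonization cultures that Section 5b does not clearly remove would push it back up.

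**5. If early cases do respond.** With ratio r among them, observed ratio = f × r + (1 − f) × 0.727. At r = 0.727 there is no dilution. At r halfway to 1 (0.864) and f = 10%, the result is 0.086 + 0.655 = 0.741, half the shift shown above.

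**The case against.** **The text is not self-contradictory.** Section 13 describes the 24 hours as an inclusion criterion, which decides who counts as exposed. Section 6b.3 speaks only of potential cases, and Section 3 presents the endpoint as clinical incidence from routine cultures, not proven transmission. This is fair as far as it goes. For in-room cultures, however, the rule still does not achieve its stated purpose, and no later step separates potential cases from plausible ones.

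**The direction is not shown.** A reader might infer that the rule necessarily pulls the ratio toward 1. The SAP does not support that. Each strategy applies to a whole hospital for a whole period (Sections 4a and 4d), and patients may have several exposures (Section 3). Someone moved in on day 5 may have acquired the organism in another room cleaned under the same strategy, so the case can respond to it. Chance imbalance across nine hospitals could also move the ratio either way. This stands.

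**The size is unknown.** A reader might put the share at a fifth or more, for instance by counting all in-room cultures in the first 48 hours. That overlooks the infections Section 5b already removes in direct admissions, and rests on room-stay figures that the SAP does not give. This stands too.

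**A stricter rule can discard real acquisitions.** Suppose 10% of cases are removed and only half are truly unrelated to the room. Removal leaves 77.1% Poisson power; keeping them (f = 5%) leaves 76.9%, so nothing is gained. If only 30% are unrelated (f = 3%), keeping them gives 78.7%, and removal costs power. A 48-hour lag as the primary rule is therefore not clearly better, and the 48 hours in Sections 5b and 6d concern hospital stay, not room entry.

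**Conclusion.** The point holds as a gap in the primary case definition. Section 6b.3 sets no minimum time from room entry to culture, and Section 5b closes it only for infections diagnosed within 48 hours of hospitalization. Patients moved into a seed room later, and possibly early colonization cultures, remain.

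The consequence is conditional. If such cases are about equally frequent across strategies and unaffected by them, a 5% or 10% share moves the planned ratio from 0.727 to about 0.741 or 0.755 and lowers power by roughly 4 to 9 percentage points under either calculation. Any response of these cases to the hospital-wide strategy makes the shift smaller. Without the actual share, the SAP supports neither an unconditional statement of bias toward 1 nor a claim that the effect is large.

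**What to change.** In Section 6b.3, require the existing 24 hours of seed-room exposure to come before collection of the qualifying culture. This uses the plan's own threshold and brings the rule into line with Section 13.

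If the primary definition is kept, add a labelled sensitivity analysis for both primary endpoints. It should exclude cases whose culture was taken less than 24 hours after room entry and, as a second cut, less than 48 hours. Those stays should also leave the exposure-day denominator, as Section 6b.4 requires. Report the number of cases removed under each strategy, which shows directly whether the share is material and whether it is balanced.

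The work is a change of wording and a date-time filter on the bed-flow and microbiology data that Section 3a already combines. The price is a somewhat smaller case count, possibly losing a few true early acquisitions. The SAP describes the study period as over and one sensitivity analysis as already done, so if the data are in hand the new analysis must be labelled post hoc.
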